Outcome Measure Description: Patient-reported eye appearance will be assessed by patient completion of the FACE-Q Eye Module Survey. These surveys have a total raw score of 7 (worst) to 28 (best). Higher scores indicate greater satisfaction. These survey scores will be

assessed individually. Additionally patients will be queried regarding their perception of the drop including changes in eye appearance before or after drop instillation. Outcome Measure Timeframe: Baseline prior to drop administration, Day 1

Adverse Events and Serious Adverse Events

Treatment-emergent adverse events, defined as any event not present prior to the initiation of the drug treatment or any event already present that worsens in either intensity or frequency following exposure to the drug treatment, will be monitored and reported throughout the study. Treatment emergent adverse scale will be graded as the following:

- Mild: Transient or mild discomfort (<48 hours) to the subject; no medical intervention/therapy required.

- Moderate: Mild to moderate limitation in activity of the subject; no or minimal medical intervention/therapy required.

- Severe: Marked limitation in activity of the subject, some assistance usually required; medical intervention/therapy required including possible hospitalization.

Serious adverse events are defined as those which result in death, hospitalization, persistent or significant incapacity or substantial disruption of the ability to conduct normal life functions (aka disability), or congenital anomaly / birth defect.

Previously reported treatment-emergent adverse effects are described further in the risks section below.

Withdrawal of Subjects

Patients may withdraw at any time at their discretion. Subject withdrawn from and/or terminated from research with or without their consent are those who are found to not meet inclusion/exclusion criteria, and/or are not able to complete the research protocol in its entirety, as well as those who suffer a treatment-emergent adverse effect requiring medication discontinuation. For any subjects who withdraw from research, including partial withdrawal from procedures, study data of the withdrawn subject will not be included in statistical analysis and will be shredded.

Data and Specimen Banking*

Not applicable.

Data Management*

Steps to Secure Data

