The study coordinator will assign each patient a specific ID number and place this information on a separate spreadsheet. The study coordinator will collect the sex, patient's age, and dates of service, but no other identifiable information. No names will be used in the forms. Presentations and publications will not identify individual patients. Data from the subjects' medical records will be encrypted and stored securely as detailed below. Identifiable data will not be stored for future use beyond the timeframe of this study. The release of data will be only to study members and no other outside organization. Data will be kept under lock and key in [name] office at the Bascom Palmer Eye Institute Oculoplastics Research Laboratory on the 4th floor ([name]), data encoded in the computer will be password-protected and will be available only to study personnel, and protected health information will not be re-used or disclosed for other purposes. Study members will be trained on how to log in and log out of the computers. The study coordinator will assign each patient a specific ID number and the sex, patient's age and date of on a separate spreadsheet. The study coordinator will record the study results with the specific sample ID on another spreadsheet.

Statistical Analysis Plan

Statistical analysis will be performed by the researchers. A paired t-test will be used to analyze the difference in palpebral fissure height, eye redness, and patient-reported eye appearance as measured through the FACE-Q survey. 114 subjects will be required to perform perimetric statistics. Chi-squared testing will be used to assess categorical variables. P <0.05 will be considered significant.

Risks to Subjects*

The primary risks to the subjects are adverse reactions to the medication. These risks are explained to patients prior to their arrival to the Oculoplastics Clinic. Previously described potential adverse reactions to include instillation site discomfort, punctate keratitis, and blurry vision although in general is well-tolerated.^{21–23,33} Potential psychosocial risks to subjects include time taken from their day to undergo tests, potentially missing work, and anxiety or discomfort from the eye drop instillation process. This study is not collecting sensitive information, thus no potential risk to reputation or legal risks should occur.

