Subjects will be instructed to call immediately for an appointment if they notice a change in their vision, eye redness, or the development of pain in either eye. Care will be taken by all study members to prevent the occurrence of any adverse events.

There are no well-controlled studies of oxymetazoline in pregnant women, and the risks to the fetus or embryo are unknown/unforeseen. One prior publication reported possible renal collecting system abnormalities after using inhaled oxymetazoline³⁴; however, another larger prospective study found no increased risk of malformations associate with nasal inhalant use including oxymetazoline,³⁵ and no alterations in maternal or fetal circulation were found to be associated with oxymetazoline use.³⁶ No studies have been performed evaluating topical oxymetazoline ophthalmic solution. Oxymetazoline is classified as US FDA pregnancy category C.

• US FDA pregnancy category C: Animal reproduction studies have shown an adverse effect on the fetus and there are no adequate and well-controlled studies in humans, but potential benefits may warrant use of the drug in pregnant women despite potential risks.

Participants will be informed of the above information and reserve the right to decline participation in the study. We will not be following pregnancy outcomes.

Unanticipated problems or complications will be reported to the IRB according to posted guidelines.

Risks of the study are listed above and will be minimized by the following:

- Study will be discontinued if subjects experience any negative effect from the medication
- Patients with a known sensitivity or history of adverse reaction to oxymetazoline or similar medications will be excluded from the study

As with any study, there is a risk of confidentiality breach. The research members will assign each patient a specific ID number and place this information on a separate spreadsheet. No names will be used in the forms. Presentations and publications will not identify individual patients.

Potential Benefits to Subjects*

There will be no direct benefit to patients participating in the study. Their involvement may provide satisfaction for aiding in future research, particularly if they would be interested in personally using the agent to increase their own palpebral fissure height or eye redness in the future.

Vulnerable Populations*

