Bascom Palmer employees and Miller School of Medicine students are considered vulnerable populations as they would be invited to participate in the study if they were interested.

Setting

Study location will be at the Bascom Palmer Eye Institute.

Resources Available

Principal investigator will be in charge of the studies and has been involved in multiple human clinical trials at the University of Miami.

Resident physicians have extensive experience in clinical research, slit lamp examination, and obtaining clinical photographs, and data collection and analysis.

Research fellow at the Bascom Palmer Eye Institute has experience with data collection and analysis.

Prior Approvals

None.

Recruitment Methods

[name], the principle investigator of this study, will assess patients for study eligibility by reviewing the medical record. These patients will be coming in during their normal visit at the Bascom Palmer Eye Institute Oculoplastics Clinic. [name] will ask eligible patients if they are interested in hearing about the study. No phone calls for recruitment will be made prior to the regular clinic visit. Other subjects may additionally be referred from other providers within the Bascom Palmer Eye Institute during their regular visits. Bascom Palmer employees and University of Miami Miller School of Medicine students would also be invited to participate if interested. No payment will be provided to patients for their participation.

Subjects who qualify for the study and express an interest in participating will have the study explained to them by a research study member and have the opportunity to ask questions. They will receive information on risks and benefits to research participation. They will receive a copy of the consent form and if desired may be able to take the consent form home prior to signing for further consultation. Those who are interested in participation will be given a scheduled appointment to meet with research staff.

Local Number of Subjects

The goal of this pilot study is to assess the ability of UpneeqTM in patients as an agent to increase eyelid height as well as possibly improve eye redness and patient-reported eye appearance. The time and resource constraints of our current pilot study allow for only approximately 114 participants.

Confidentiality

Check all that apply:

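### Does making 114 both the required number and the resource limit, with withdrawn subjects dropped, leave the trial short of its own requirement?

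*Combined protocol and SAP*

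**What the plan says.** Four places in the combined protocol and SAP bear on the number.

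- **Statistical Analysis Plan:** "114 subjects will be required to perform perimetric statistics". No power, effect size, SD, allocation ratio or loss rate accompanies it. The test named just before it is a paired t-test, with significance at P < 0.05.
- **Local Number of Subjects:** "The time and resource constraints of our current pilot study allow for only approximately 114 participants".
- **Withdrawal of Subjects:** subjects may leave at any time. Subjects are also withdrawn if they prove ineligible, if they "are not able to complete the research protocol in its entirety", or if they are among "those who suffer a treatment-emergent adverse effect requiring medication discontinuation". For anyone withdrawn, "study data of the withdrawn subject will not be included in statistical analysis and will be shredded".
- **Risks to Subjects:** "Study will be discontinued if subjects experience any negative effect from the medication". The same section gives the known reactions: "Previously described potential adverse reactions to include instillation site discomfort, punctate keratitis, and blurry vision".

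Procedures Involved describes one application of drops to both eyes, then photographs and a survey at 2 hours. No study follow-up is added after that.

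**The concern.** A number required for the statistics reads most naturally as the number analysed. If about 114 is also all the site can enrol, the minimum and the ceiling coincide and there is no margin. Withdrawals are foreseen and their data are dropped, so a single loss would put the trial below its own stated requirement. The plan does not say whether 114 counts subjects enrolled or analysed, or whether a lost subject is replaced.

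The sentence in Risks to Subjects adds to the doubt. Its trigger is any negative effect, which is wider than the trigger in Withdrawal of Subjects, and its grammatical subject is the study. If it meant the whole trial, one expected mild reaction could end enrolment far below 114. Staff following different sections could then finish with different numbers, and a reader could not tell whether the requirement had been met.

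**Working it through.** **The plan's own figure.** 114 cannot be reproduced, because the inputs are not given. It can only be solved backwards. With two-sided alpha 0.05 and 80% power (both assumed), 114 pairs detect 0.265 SD in a paired test, and 57 per arm detect 0.529 SD of change in a two-sample test.

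**Inputs.** N = 114 and alpha 0.05 come from the Statistical Analysis Plan section. The two arms come from Procedures Involved. Allocation of 1:1 (57 per arm), two-sided testing, 80% power and all loss or reaction rates are assumptions.

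**Margin.** 114 required − about 114 feasible = about 0. One loss gives 114 − 1 = 113. If each subject has the same independent risk q of being lost, the chance of losing nobody is (1 − q)^114:

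- q = 1%: 0.99^114 = 0.318
- q = 2%: 0.98^114 = 0.100
- q = 5%: 0.95^114 = 0.003

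So, on the strictest reading, the requirement would probably be missed even at low loss rates. The question is whether missing it matters.

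**Cost of subject-level losses.** The detectable difference in SD units is close to (t₀.₉₇₅ + t₀.₈₀) × √(1/n₁ + 1/n₂), with n₁ + n₂ − 2 degrees of freedom. For 57 and 57: (1.981 + 0.845) × 0.1873 = 0.529. The exact noncentral-t values are:

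| Analysed (drug / saline) | Situation | Detectable difference (SD) |
|---|---|---|
| 57 / 57 | no loss | 0.529 |
| 56 / 57 | one loss | 0.532 |
| 54 / 57 | 5% of drug arm | 0.537 |
| 51 / 57 | 10% of drug arm | 0.545 |
| 51 / 51 | 10% of both arms | 0.560 |

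If 114 was set for 80% power, the two-sample power is 0.796 after one loss, 0.779 at 5% loss overall and 0.757 at 10%. For the paired test the figures are 0.796, 0.778 and 0.754.

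**Enrolment needed to keep 114 analysed, in expectation.** 114/0.99 = 115.2, so 116. 114/0.95 = 120. 114/0.90 = 126.7, so 127. The first is within any fair meaning of approximately 114; the last two may not be.

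**Whole-study reading of the Risks sentence.** The chance that none of 57 drug-treated subjects reacts is 0.99^57 = 0.564 at a 1% rate, 0.98^57 = 0.316 at 2% and 0.95^57 = 0.054 at 5%. The median drug-treated subject at whom the first reaction occurs is ln 0.5 / ln(1 − q), rounded up:

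- 1%: the 69th, beyond 57, so the trial more likely than not completes
- 2%: the 35th, about 70 subjects in all, detectable difference 0.68 SD
- 5%: the 14th, about 28 in all, 1.10 SD

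These are the only large figures, and they depend entirely on that reading.

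**Does the rest of the text support it?** The protocol has withdrawal criteria for individual subjects and a three-grade severity scale whose mildest grade is transient discomfort needing no treatment. It also reports treatment-emergent events throughout the study. These provisions have little purpose if the first mild reaction closes the trial. Nor does any section remove a subject from the analysis merely for a mild reaction. The data rule applies to withdrawn subjects, and the exclusion in Risks to Subjects concerns sensitivity known before entry.

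**The case for a change.** The best case for a change is that the text literally makes 114 a minimum, makes about the same number a ceiling, and then plans to lose data. No derivation is available to settle what 114 means, and a few words would remove the doubt. The Risks sentence, as written, does say the study stops, and its trigger is a reaction that the protocol itself expects.

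Part of this stands. There is no loss allowance or replacement rule, and the plan does not say whether 114 is enrolled or analysed. The two triggers do differ: one is "Study will be discontinued if subjects experience any negative effect from the medication", the other covers "those who suffer a treatment-emergent adverse effect requiring medication discontinuation". Those two passages must be reconciled. That is a point of clinical conduct, and nothing is said here about which rule should hold.

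The claimed conflict over the number does not stand. Local Number of Subjects says approximately, so it is not a hard ceiling. The sentence in the Statistical Analysis Plan section is too loose to bear the weight of a hard minimum: it speaks of perimetric statistics although no visual-field test is planned, which looks like a slip for parametric. A t-test can be run on 113 or 108 subjects as well as on 114. After a single drop, a subject with brief discomfort can still be photographed at 2 hours.

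**Conclusion.** No change to the plan is needed. The two statements fit together as one approximate enrolment target fixed by resources. An analyst would enrol about 114, analyse those who complete and report both counts. With losses of up to 10%, the detectable difference rises from 0.53 SD to at most 0.56 SD, and an assumed 80% power falls to about 75 or 76%. Neither would alter how the results are read.

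This rests on 1:1 allocation, a two-sided 5% test, assumed loss rates (the documents give none) and the subject-level reading of the Risks sentence, which the surrounding text favours. If that sentence were applied to the whole trial, the loss could be large. That possibility comes from how a conduct sentence is worded, not from a fault in the sample size. The conclusion concerns the count only. It does not address whether 114 is adequate, whether the paired test is the right comparison, or whether dropping withdrawn subjects' data could bias the result.

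### Risks to Subjects and Withdrawal of Subjects give different units and triggers for discontinuation, which leaves open whose data are collected and kept

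*Combined protocol and SAP*

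**What the plan says.** Three parts of the protocol bear on what happens after an adverse reaction.

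- **Risks to Subjects**, in the list of measures that reduce risk: "Study will be discontinued if subjects experience any negative effect from the medication". The bullet gives no grade, no count and no decision-maker.
- **Adverse Events and Serious Adverse Events**: treatment-emergent events "will be monitored and reported throughout the study". The lowest of three grades is "Transient or mild discomfort (<48 hours) to the subject; no medical intervention/therapy required".
- **Withdrawal of Subjects**: "Patients may withdraw at any time at their discretion". Subjects are also withdrawn or terminated if they do not meet the eligibility criteria or "are not able to complete the research protocol in its entirety", "as well as those who suffer a treatment-emergent adverse effect requiring medication discontinuation". The section ends with a data rule. It opens "For any subjects who withdraw from research, including partial withdrawal from procedures" and concludes that "study data of the withdrawn subject will not be included in statistical analysis and will be shredded".

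Procedures Involved describes a baseline survey and photograph, one application of drug or saline to both eyes, a 2-hour wait, and then a second photograph and survey. No further dose is described.

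**The concern.** The bullet under Risks to Subjects and the withdrawal section answer the same question differently. One names the study and reacts to any unwanted drug effect. The other names the subject and requires an effect that makes stopping the drug necessary. From the text, staff and the IRB cannot tell whether a minor reaction ends the trial, ends one person's participation, or is simply graded and recorded.

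The choice also reaches the analysis. It can decide whether the 2-hour primary outcome is measured. Through the data rule that closes the withdrawal section, it can also decide whether anything from that subject is kept. Exclusion would then depend on something that happens after randomisation and may be caused by the treatment, so the arms being compared might no longer be the arms as randomised.

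**Working it through.** The plan gives no threshold, rate or probability here, so there is no stated figure to reproduce. The check is a comparison of the sections, followed by an illustration of size.

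1. **Unit.** Risks to Subjects: the study. Withdrawal of Subjects: the individual. No sentence says that the first means the second.

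2. **Trigger.** Risks to Subjects: any unwanted effect of the drug. Withdrawal of Subjects, on adverse-effect grounds: only "as well as those who suffer a treatment-emergent adverse effect requiring medication discontinuation". The first is broader even if both are read per subject.

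3. **Overlap.** Risks to Subjects lists instillation-site discomfort and blurred vision as known reactions. Brief discomfort can meet the mild grade and also satisfy the bullet, without satisfying the withdrawal clause. The overlap is therefore foreseeable.

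4. **What can still be discontinued.** After the single application, no dosing remains. Before 2 hours, what remains is the second photograph and survey. After those are done, no scheduled study procedure is left.

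5. **Consequence for the outcome.** Palpebral fissure height is the sum of MRD1 and MRD2 taken from the photograph. Without the 2-hour photograph there is no change score, and the subject cannot enter the paired t-test in the Statistical Analysis Plan.

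6. **Consequence for data already collected.** A subject stopped before 2 hours has not finished the procedures and so may fall under "are not able to complete the research protocol in its entirety". The next sentence orders exclusion and shredding. It speaks of subjects who withdraw, so its reach to those stopped by staff is not certain, although it directly follows a list that covers both. If it does reach them, the baseline data go, and the study record of the reaction may go too. That sits badly with events that "will be monitored and reported throughout the study".

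7. **Size, as an illustration.** The reaction rate p and the number on drug n are assumed. The total of 114 is from the Statistical Analysis Plan. The expected number of drug-arm subjects with an effect is n × p.
   - n = 57 (114/2): 57 × 0.01 = 0.57; 57 × 0.05 = 2.85; 57 × 0.10 = 5.70.
   - n = 38 (one third of 114): 0.38, 1.90, 3.80.
   - n = 76 (two thirds of 114): 0.76, 3.80, 7.60.

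   These counts include effects at any time. The loss due to the bullet is smaller. It leaves out effects first seen after the 2-hour measurements, and subjects whom the withdrawal section would remove anyway. The documents give neither share. At the assumed rates the counts are therefore ceilings on the expected drug-arm loss and do not estimate it.

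**The case against.** The strongest reply is that the bullet is loose wording for ending the affected person's participation. It stands in a list of protective measures, the next item plainly concerns individual patients, and the withdrawal section removes only the affected subject even when the drug must be stopped. A lesser effect closing the whole trial would fit poorly with that. This stands: the trial-wide reading is the less plausible one, though no sentence rules it out. The reply settles the unit and leaves the trigger unreconciled.

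Three further points limit the concern.

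- Grading mild events is not itself a conflict, since a protocol can grade an event and also act on it. The mismatch is with the withdrawal clause.
- A reader might infer that the loss must fall on the drug arm, because the bullet refers to drug effects. The documents do not establish this. Procedures Involved states blinding only for the person doing the analysis and does not describe masking of examiner or subject. No section says how an effect is attributed to the drug. Risks to Subjects also mentions discomfort from the instillation itself, which saline could cause. A heavier loss on drug is plausible but not certain.
- The exclude-and-shred sentence is a problem whatever the bullet says, and a subject with baseline values alone adds nothing to a paired test. Both are true. The sentence still belongs here, because it turns a broad discontinuation trigger into lost data. Retention by itself mainly protects safety reporting. The efficacy analysis gains only if the 2-hour measurements are also taken.

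**Conclusion.** The inconsistency is real and rests on the wording alone: the unit and the trigger differ, and the more charitable reading resolves only the unit. The consequence for the analysis is conditional. It needs a subject-level reading, an effect before the 2-hour measurements that the withdrawal section would not already have acted on, and, for the loss of data already collected, that the subject counts as withdrawn. Its size cannot be derived from the documents and could be small.

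Two stronger conclusions are tempting and are not supported.

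- A reader might infer that the trial would probably stop early. With 57 on drug, the chance of at least one effect is 1 − (1 − p)^57, which is 44% at p = 1% and 95% at p = 5%. Those rates are assumed, and the calculation uses the less plausible reading.
- A reader might infer that the analysed data would contain nobody who reacted. That follows only if every such subject is treated as withdrawn, including those whose effect appears after their measurements are complete.

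The point should be corrected, with medium confidence in its practical weight. Which rule is clinically right is not a question for this review.

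**What to change.** 1. Reconcile Risks to Subjects and Withdrawal of Subjects into one rule that states its unit (trial or subject) and its trigger. The clinical content is for the investigators and the IRB.
2. Amend the exclude-and-shred sentence so that data already collected from a subject discontinued for an adverse effect are kept, subject to consent. The event goes into the safety reporting, and any available outcome data go into the efficacy analysis.
3. State whether the 2-hour photograph and survey are still collected from such a subject.

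The cost is a short wording amendment and IRB review. None of the changes alters the sample size or adds a visit.
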